8.2 Domain Derivations

Refer to BMS internal documents for additional conventions, such as on date imputation and on derivation of parameters, across study periods for standard data domains: AEs, demography, ECGs, laboratory test results, non-study medications, physical measurements, subject status, and vital signs.^{3,4,5,6,7,8,9,10,11,12,13} These documents are available upon request.

Duration of organ support

1) Rules to calculate vasopressor use

Following vasopressors are recorded

- a) Dopamine
- b) Epinephrine
- c) Norepinephrine (Levophed)
- d) Vasopressin
- e) Phenylephrine (NeoSynephrine)

Dobutamine is not a vasopressor for this determination. If a patient receives any of the 5 vasopressors listed above on a calendar day, then it is counted as a vasopressor day.

2) Rules for duration of Mechanical Ventilation (MV)

- a) We define MV as invasive ventilation only; it does not include non-invasive techniques such as continuous positive airway pressure (CPAP) or bi-level positive airway pressure (BiPAP) mask ventilation.
- b) Duration of MV is the number of consecutive* days of invasive mechanical ventilation that a subject requires.

i) *If a subject is free of MV for < 48hrs (or 2 days when hours are not recorded) these days are counted as part of the overall duration of MV should the participant be assisted with MV.

(1).If free of MV for < 48 hrs, this will count as part of one episode, however if free for > 48 hrs, this will count as an independent episode

References: <http://www.trialsjournal.com/content/12/1/79>

<http://www.nejm.org/doi/full/10.1056/NEJMoa1005372#t=articleTop>

ii) Use calendar day for all calculations. If a subject receives MV for a few hours (intubated late at night or extubated early in the morning), each calendar day is included in the calculation.

3) Rules for Renal Replacement Therapy (RRT)

- a) Types of renal replacement therapy (RRT) in this measurement include peritoneal dialysis, continuous renal replacement therapy (CRRT), and hemodialysis (HD).
- b) Duration of RRT is defined as the amount of consecutive* days that a subject requires RRT.

- i) *If a subject is free of RRT for < 72hrs (or 3 days when hours are not recorded) these days are counted as part of the duration of RRT
- c) “Duration of renal support will be defined as the number of days from initiation of RRT to final dialysis treatment. Duration of renal support will be censored if the patient is still dialysis dependent at the time of death” or hospital discharge.
- d) Reference: <http://www.nejm.org/doi/full/10.1056/NEJMoa0802639>
- e) The duration of dialysis is recorded as 0 if subjects received chronic dialysis prior to hospital admission.

9 CONTENT OF REPORTS

9.1 Planned Analyses

- The final analysis will be performed after all subjects have completed Day 90 on treatment.

9.2 Listings

Reports also contain listings described in the Data Presentation Plan (DPP). Listings are sorted by Subject ID, as applicable. Select listings display dosing status according to the GBS standard temporal dosing model.¹⁴

10 CONTENT OF REPORTS

The analyses described in this SAP will be included in clinical study report.

APPENDIX 1 RELEVANT PROTOCOL DEVIATIONS

The relevant protocol deviations that can be programmed from the database are identified below.

The list would be updated as appropriate if, in the course of monitoring the study, additional protocol deviations are found and considered relevant.

- Age < 18 years;
- Patient does not have documented or suspected infection prior to study drug administration;
- Patient does not have at least 1 new organ dysfunction prior to study drug administration;
- Patient does not have absolute lymphocyte (ALC) values </= 1100 cells/uL prior to study drug administration;
- Patient is not in ICU at time of study drug administration;
- Medical history of autoimmune disease;
- Medical history of bone marrow or solid organ transplant;
- Body Weight \leq 50 kg or \geq 180 kg;
- Exposure to nivolumab or to an anti-PD-1, anti-PD-L1, anti-PD-L2, anti-CD137, anti-CTLA-4 antibody, or any other antibody or drug specifically targeting T-cell co-stimulation or checkpoint pathways (#);
- Exposure to GM-CSF (Granulocyte-macrophage colony-stimulating factor; Sargramostim; Leukine) within 4 weeks or 5 half-lives (whichever is longer) of study treatment administration;
- Incorrect dosing or study treatment assignment.

Non-study medications marked above with # are identified by a BMS physician prior to database lock.

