#### 2) Type of Participant and Target Disease Characteristics

- a) Men and women ages  $\geq 18$  years old
- b) Participant has documented OR suspected infection
  - i) Documented infection is infection confirmed with a microbiologic diagnosis
  - ii) Suspected infection is infection being treated with ongoing antimicrobial therapy at the time of study treatment administration
- c) Participant has the onset of severe sepsis or septic shock at least 24 hours prior to study treatment administration based on having at least 1 of the 3 organ dysfunction criteria below. Organ dysfunction must be new and thought to be due to sepsis.
  - i) Hypotension defined as the need for treatment with any vasopressor(s) for at least 6 hours to maintain a systolic pressure  $\geq 90$  mmHg or a mean arterial pressure  $\geq 70$  mmHg  
OR
  - ii) Acute respiratory failure defined as the need for invasive mechanical ventilation for at least 24 hours to support pulmonary function  
OR
  - iii) Acute kidney injury defined as creatinine  $> 2.0$  mg/dL (from a creatinine that was within the normal reference range prior to onset of sepsis) OR urine output  $< 0.5$  mL/kg/hr for  $> 2$  hours despite adequate fluid resuscitation. In the presence of pre-existing impairment of renal function (defined as a serum creatinine concentration  $> 2$  times the upper limit of the normal reference range prior to the onset of sepsis), the participant should meet 1 of the other 2 organ dysfunction criteria above.
- d) Participant has sepsis-associated immunosuppression based on an absolute lymphocyte count  $\leq 1100$  cells/ $\mu$ L on at least one assessment within the 96 hours prior to study treatment administration
- e) Participant is in an intensive care unit at the time of study treatment administration and, based on their medical condition, there are no plans to discharge from the ICU in the next 24 hours
- f) Participant Re-enrollment: This study permits the re-enrollment of a participant who has discontinued the study as a pre-treatment failure (ie, participant has not been randomized /has not been treated). If re-enrolled, the participant must be re-consented.

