## 6.2 Exclusion Criteria

### 1) Medical Conditions

- a) Previous episode of severe sepsis or septic shock with ICU admission during the current hospitalization
- b) Active, known, or suspected autoimmune disease **NOTE:** Participants with type I diabetes mellitus, hypothyroidism only requiring hormone replacement, skin disorders (such as vitiligo, psoriasis, or alopecia) not requiring systemic treatment, or conditions not expected to recur in the absence of an external trigger are permitted to enroll.
- c) History of solid organ or bone marrow transplant.
- d) Known history of malignancy and has undergone treatment for such within 6 weeks prior to study treatment administration.
- e) Known history of infection with HIV and not on antiretroviral therapy prior to the current hospitalization or  $CD4 \leq 200$  cells/mm^3 or AIDS-defining illness in the past year.
- f) Known history of chronic HBV infection and not on treatment with an HBV nucleos(t)ide analogue prior to the current hospitalization or HBV DNA > 100 IU/mL.
- g) Known history of infection with HCV and currently undergoing treatment for HCV infection or has detectable HCV RNA.

- h) Known active illicit drug use disorder (defined as illicit drug use on 5 or more days in the past 30 days) OR known active alcohol use disorder (defined as drinking 5 or more alcoholic drinks on the same occasion on 5 or more days in the past 30 days)
- i) Any other sound medical, psychiatric and/or social reason as determined by the investigator

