## **7.8 Concomitant Therapy**

### **7.8.1 Prohibited and/or Restricted Treatments**

Prohibited and/or restricted medications taken prior to study treatment administration or during the study are described below. Medications administered during the index hospitalization within

1 week prior to study treatment administration must be recorded on the CRF. Any concomitant therapies must be recorded on the CRF.

- 1) During the study, immunosuppressive agents are prohibited unless utilized to treat a drug related adverse event. **NOTE:** Adrenal replacement steroid doses up to the equivalent of hydrocortisone 300 mg/day for the treatment of septic shock are permitted.

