7.2 Study Conduct

Relevant protocol deviations are summarized by treatment and total for treated subjects. Relevant protocol deviations are those that are programmable and could potentially affect the interpretability of the study results, such as:¹

- Certain inclusion or exclusion criteria;
- Incorrect dosing or study treatment assignment;

- Use of prohibited concomitant medications;
- Subjects remaining on treatment/in the study despite having met specified criteria for withdrawal.

A subject is considered to have a deviation of an inclusion or exclusion criterion only if all pre-treatment measurements fail the criterion. The consent date defines the beginning of enrollment. [Appendix 1](#) describes the relevant protocol deviations that can be programmed from the database.

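### Three of the SAP's programmed deviation rules do not match the eligibility criteria they check, and prohibited concomitant medication has no rule at all

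*SAP*

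**What the plan says.** SAP 7.2 defines relevant deviations as those that can be programmed and could affect how the results are interpreted. It gives four example categories, one of which is "Use of prohibited concomitant medications", and sends the reader to Appendix 1 for the programmed list. It also says that an eligibility criterion counts as violated only when every pre-treatment measurement fails it.

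Appendix 1 includes these three lines:

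- "Medical history of autoimmune disease"
- "Patient does not have absolute lymphocyte (ALC) values </= 1100 cells/uL prior to study drug administration"
- "Patient does not have at least 1 new organ dysfunction prior to study drug administration"

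The protocol criteria behind them are narrower. Exclusion 1b in Protocol 6.2 covers active, known or suspected autoimmune disease, but its note allows enrolment of "Participants with type I diabetes mellitus, hypothyroidism only requiring hormone replacement, skin disorders (such as vitiligo, psoriasis, or alopecia) not requiring systemic treatment", and also of conditions not expected to recur without an external trigger. Inclusion 2d in Protocol 6.1 requires the low lymphocyte count "on at least one assessment within the 96 hours prior to study treatment administration". Inclusion 2c begins "Participant has the onset of severe sepsis or septic shock at least 24 hours prior to study treatment administration".

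On medication, Protocol 7.8.1 states "During the study, immunosuppressive agents are prohibited unless utilized to treat a drug related adverse event", and a note permits adrenal replacement steroids up to a stated dose for septic shock. Appendix 1 has two drug-exposure lines, for checkpoint-pathway agents and GM-CSF. Both restate eligibility exclusions; neither concerns medication prohibited during the study.

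**The concern.** A deviation table tells the reader whether the intended population was enrolled and treated as planned. If a rule is broader than its criterion, correctly enrolled participants are reported as deviations. If it is looser, real violations go unreported.

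The two missing time conditions are not incidental. Protocol 3.3 presents onset at least 24 hours before dosing, together with a depressed lymphocyte count, as the eligibility-based way of keeping out participants still in the early pro-inflammatory phase. The 24-hour condition is therefore part of the stated risk mitigation, and the programmed check does not test it.

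The medication gap is an inconsistency within the SAP: Section 7.2 names the category and points to a list that does not contain it. It is relevant because mHLA-DR expression and absolute lymphocyte count are secondary endpoints, and treatment with immune-modulating medication is part of the immune-mediated AE definition in SAP 7.7.5.

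**Working it through.** There is no stated figure to reproduce. The check sets each rule beside its source and then runs constructed participants through both.

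**Side by side**

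| Item | Protocol | SAP Appendix 1 | Direction of error |
|---|---|---|---|
| Autoimmune disease | 6.2, 1b: excluded, with named exceptions | Any history, no exceptions | Flags eligible participants |
| Lymphocyte count | 6.1, 2d: at or below 1100 at least once in the last 96 h | At or below 1100 at any time before dosing | Can miss a violation |
| Organ dysfunction | 6.1, 2c: onset at least 24 h before dosing | New dysfunction at any time before dosing | Can miss a violation |
| Prohibited medication | 7.8.1: immunosuppressants, with permitted uses | No line, although SAP 7.2 names the category | Misses the deviation |

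The age, transplant, body-weight, checkpoint-agent and GM-CSF lines agree with the protocol. The GM-CSF line keeps its time window, so the list is able to carry one.

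**How much time the lymphocyte rule leaves open.** Screening may run 10 days (Protocol Table 2.-1, footnote a): 10 × 24 = 240 h. The criterion covers the last 96 h. 240 − 96 = 144 h in which a low value satisfies the SAP rule but not the protocol.

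**Constructed participants** (otherwise eligible)

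| Case | Protocol | Appendix 1 |
|---|---|---|
| History of type I diabetes, or of psoriasis without systemic treatment | Eligible | Flagged |
| Count 900 at −200 h, then 1500 at −60 h and −12 h | Violation | Not flagged |
| Organ dysfunction starting 10 h before dosing | Violation | Not flagged |
| Prohibited immunosuppressant during the study | Deviation | Not flagged |
| Active autoimmune disease outside the exceptions | Violation | Flagged |
| Fully eligible | None | Not flagged |

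The lymphocyte case fails the protocol whether inclusion 2d is applied or the rule in Protocol 6.4.1 that the most current result before randomization decides, since both later values are 1500.

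**Weight of one participant.** With the planned maximum of 15 per arm, 1/15 = 6.7%; over 30 in total, 1/30 = 3.3%. That is the shift in the row for the deviation concerned. The row for any deviation moves only if that participant has no other flag.

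**The case against.** The best defence is that Appendix 1 gives short labels, not code. SAP 7.2 promises only certain criteria, limited to what can be programmed, and Appendix 1 says the list will be updated if further deviations are found. Several of the missing details are hard to program. Protocol Table 2.-1 asks for start dates, not times, of ventilator, vasopressor and dialysis use, and SAP 8.2 allows for hours not being recorded. The autoimmune exceptions and the permitted immunosuppressant uses turn on indication, dose or medical judgement.

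Part of this stands. Criteria that are simply absent from Appendix 1, such as those on HIV or resuscitation orders, are not errors. The same goes for the 7.2 category on staying in the study despite withdrawal criteria, which matters little after a single dose. Some checks will need dates or manual review. But the three lines at issue were selected and then worded differently from their criteria. The update clause provides for additions; it does not correct existing lines. The physician identification marked # applies only to the checkpoint-agent line.

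A reader might infer three stronger things, and the documents support none of them:

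- *That immunosuppressant use would be hidden.* SAP 7.5.2 summarizes concomitant medication by arm and immune-modulating medication separately, and SAP 7.7.5 tabulates immune-mediated events where such medication was started. What is missing is the classification as a deviation, because those summaries do not separate prohibited from permitted use.
- *That the rule requiring all measurements to fail is itself wrong for the lymphocyte count.* A criterion met by at least one qualifying value is failed only when none qualifies, which is the same logic. Only the window is missing.
- *That lymphocyte misses would be common.* Baseline labs must fall within 48 hours before dosing, so each participant should have an in-window count. A miss needs a low value only before the 96 hours and every later value above 1100.

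**Conclusion.** The mismatch is real and minor. Followed as written, one rule reports eligible participants as deviations, two can pass participants who violate a criterion, and one category named in SAP 7.2 is never checked. This rests on reading the Appendix 1 lines literally; derivation documents that the SAP cites but does not reproduce might supply the missing conditions.

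The consequence is limited to the accuracy of a descriptive table. Deviations are tabulated by treatment and total, and none of the populations in Protocol 10.2 or SAP 6.3 is defined by them. It would be wrong to infer that a safety, pharmacokinetic, receptor-occupancy, mHLA-DR or lymphocyte result changes. Each misclassified participant shifts a deviation row by about 6.7 percentage points in a 15-person arm, but the documents give no basis for the number affected, so that figure is a unit of error and not an estimate of it.

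**What to change.** Before database lock, revise SAP Appendix 1 as follows:

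1. **Autoimmune line.** Take out the conditions permitted by the note to exclusion 1b. Use physician review for the exceptions that need judgement, extending the step already marked # for the checkpoint-agent line.
2. **Lymphocyte line.** Restrict it to the 96 hours before dosing, and apply the SAP 7.2 rule that all measurements must fail only to values in that window.
3. **Organ-dysfunction line.** Add onset at least 24 hours before dosing. Where clock times are not recorded, use dates, with manual review of cases that dates cannot settle.
4. **New line.** Add immunosuppressants prohibited under Protocol 7.8.1, leaving out the uses that section permits, with physician review.

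The cost is a few lines of SAP text and programming, plus some manual review among about 30 participants. Protocol 7.8.1 already requires concomitant therapies to be recorded on the CRF, so item 4 should need no new medication collection. The CRF itself is not among the documents, so whether it holds onset times for item 3 cannot be confirmed.

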APPENDIX 2 IMMUNE MEDIATED ADVERSE EVENTS DEFINITION AND CONVENTIONS

Immune-Mediated Adverse Event Definition

Category	Preferred Terms
ADRENAL INSUFFICIENCY	ADRENAL INSUFFICIENCY HYPOTHALAMIC PITUITARY ADRENAL AXIS SUPPRESSION SECONDARY ADRENOCORTICAL INSUFFICIENCY
DIABETES MELLITUS	DIABETES MELLITUS DIABETIC KETOACIDOSIS FULMINANT TYPE 1 DIABETES MELLITUS LATENT AUTOIMMUNE DIABETES IN ADULTS TYPE 1 DIABETES MELLITUS
DIARRHEA/COLITIS	AUTOIMMUNE COLITIS COLITIS COLITIS ULCERATIVE DIARRHOEA ENTERITIS ENTEROCOLITIS
HEPATITIS	ACUTE HEPATIC FAILURE ACUTE ON CHRONIC LIVER FAILURE ALANINE AMINOTRANSFERASE INCREASED ASPARTATE AMINOTRANSFERASE INCREASED AUTOIMMUNE HEPATITIS BLOOD BILIRUBIN INCREASED DRUG-INDUCED LIVER INJURY HEPATIC FAILURE HEPATITIS HEPATITIS ACUTE HEPATOTOXICITY HYPERBILIRUBINAEMIA TRANSAMINASES INCREASED
HYPERSENSITIVITY	ANAPHYLACTIC REACTION ANAPHYLACTIC SHOCK HYPERSENSITIVITY INFUSION RELATED REACTION

Immune-Mediated Adverse Event Definition

Category	Preferred Terms
HYPERTHYROIDISM	BASEDOW'S DISEASE HYPERTHYROIDISM PRIMARY HYPERTHYROIDISM
HYPOPHYSITIS	HYPOPHYSITIS HYPOPITUITARISM LYMPHOCYTIC HYPOPHYSITIS
HYPOTHYROIDISM	AUTOIMMUNE HYPOTHYROIDISM HYPOTHYROIDISM PRIMARY HYPOTHYROIDISM
HYPOTHYROIDISM/THYROIDITIS	ATROPHIC THYROIDITIS AUTOIMMUNE HYPOTHYROIDISM AUTOIMMUNE THYROIDITIS HYPOTHYROIDISM PRIMARY HYPOTHYROIDISM THYROIDITIS THYROIDITIS ACUTE
NEPHRITIS AND RENAL DYSFUNCTION	ACUTE KIDNEY INJURY AUTOIMMUNE NEPHRITIS BLOOD CREATININE INCREASED CREATININE RENAL CLEARANCE DECREASED HYPERCREATININAEMIA NEPHRITIS NEPHRITIS ALLERGIC PARANEOPLASTIC GLOMERULONEPHRITIS RENAL FAILURE RENAL TUBULAR NECROSIS TUBULOINTERSTITIAL NEPHRITIS
PNEUMONITIS	INTERSTITIAL LUNG DISEASE PNEUMONITIS
RASH	AUTOIMMUNE DERMATITIS

Immune-Mediated Adverse Event Definition

Category	Preferred Terms
RASH	DERMATITIS DERMATITIS ALLERGIC DERMATITIS EXFOLIATIVE DRUG ERUPTION ERYTHEMA MULTIFORME EXFOLIATIVE RASH FIXED DRUG ERUPTION NODULAR RASH RASH RASH ERYTHEMATOUS RASH GENERALISED RASH MACULAR RASH MACULO-PAPULAR RASH MORBILLIFORM RASH PAPULAR RASH PRURITIC RASH VESICULAR STEVENS-JOHNSON SYNDROME TOXIC EPIDERMAL NECROLYSIS TOXIC SKIN ERUPTION
THYROIDITIS	ATROPHIC THYROIDITIS AUTOIMMUNE THYROIDITIS THYROIDITIS THYROIDITIS ACUTE
